12.4 Response Criteria for Patients with Relapsed Lymphoblastic Lymphoma

12.4.1 Response Criteria

Response and progression will be evaluated in this study using the new international criteria proposed by the revised Response Evaluation Criteria in Pediatric Non-Hodgkin Lymphoma Criteria³⁴, with modification from the Lugano classification.³⁴⁻³⁶ Patients will LL must have either measurable or evaluable disease.

12.4.2 Evaluable for objective response:

Only those patients who have measurable disease present at baseline and have received at least one dose of protocol therapy will be considered evaluable for response. These patients will have their response classified according to the definitions stated below. (Note: Patients who exhibit objective disease progression prior to the end of Course 1 will also be considered evaluable.)

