Palbociclib is an orally active, potent, selective inhibitor of CDK4 and CDK6. CDK6 is highly homologous to CDK4 and can perform the same function by phosphorylating retinoblastoma protein (Rb), thus potentially creating a redundant mechanism to promote cell cycle progression. Inhibition of both enzymes is therefore necessary to ensure the greatest possible antitumor activity. Palbociclib inhibits DNA synthesis by preventing progression from the G1 to S phase of the cell cycle. Treatment of tumor cells with palbociclib inhibits Rb phosphorylation and induces growth arrest. Accordingly, a reduction in Rb phosphorylation serves as a biomarker of CDK4/6 inhibition by palbociclib.

Eligible patients will receive a single cycle of re-induction therapy. Palbociclib will be administered once daily for 21 days in combination with an established 4-drug re-induction platform. After completion of the feasibility portion of the study an expanded cohort will be enrolled at the MTD and/or recommended phase 2 dose (RP2D) of palbociclib to further assess the safety and feasibility of this regimen and to preliminarily explore the biological and clinical activity within the confines of a phase 1 study.

EXPERIMENTAL DESIGN SCHEMA

Therapy will be interrupted if there is evidence of progressive disease or drug related dose-limiting toxicity. Each patient will receive a single cycle of therapy.

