1.2 Secondary Aims

- 1.2.1 To preliminarily define the antitumor activity of palbociclib in combination with chemotherapy for children with relapsed ALL/LL within the confines of a Phase 1 study.
- 1.2.2 To assess the biologic activity of palbociclib in this patient population.

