4.1 Inclusion Criteria

- 4.1.1 Age: Patients must be ≥ 12 months and < 31 years of age at the time of study enrollment.
- 4.1.2 Diagnosis: Patients with recurrent or refractory B- or T-lineage lymphoblastic leukemia and lymphoma. Patients with leukemia must have $\geq 5\%$ (M2 or M3) bone marrow blasts with or without an extramedullary site of relapse. Morphologic relapse for M2 should be confirmed using flow cytometry, FISH and/or cytogenetics or molecular techniques. Patients with LL must have either measurable or evaluable disease.
- 4.1.3 Disease Status: Patients with first or greater relapsed T-lineage ALL or LL and second or greater relapsed B-lineage ALL or LL are eligible. Patients with primary refractory disease with at least 2 prior induction attempts or first relapse refractory to at least one prior re-induction attempt are eligible. Patients with refractory disease, however, must not have received a standard 4-drug re-induction inclusive of a steroid, anthracycline, asparaginase and vincristine in combination (e.g., UKALLR3 or AALL01P2) as their most recent prior therapy but they may have received a re-induction regimen that contain some of these agents.
- 4.1.4 Performance Level: Karnofsky $\geq 50\%$ for patients > 16 years of age and Lansky ≥ 50 for patients ≤ 16 years of age (See Appendix I). Patients who are unable to walk because of paralysis, but who are up in a wheelchair, will be considered ambulatory for the purpose of assessing the performance score.
- 4.1.5 Prior Therapy:
- 4.1.5.1 Patients must have fully recovered from the acute toxic effects of all prior anti-cancer therapy and must meet the following minimum duration from prior anti-cancer directed therapy prior to enrollment. If after the required timeframe, the numerical eligibility criteria are met, e.g., blood count criteria, the patient is considered to have recovered adequately.
- a. Cytotoxic chemotherapy or other anti-cancer agents known to be myelosuppressive. See DVL homepage for commercial and Phase 1 investigational agent classifications. For agents not listed, the duration of this interval must be discussed with the study chair and the study-assigned Research Coordinator prior to enrollment.
- A waiting period prior to enrollment is not required for patients receiving standard cytotoxic maintenance chemotherapy (i.e., corticosteroid, vincristine, 6MP, and/or methotrexate).

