11.5 Pharmacokinetic and Correlative Studies and Response Analysis

A descriptive analysis of pharmacokinetic (PK) parameters of palbociclib will be performed to define systemic exposure, drug clearance, and other pharmacokinetic parameters. The PK parameters will be summarized with simple summary statistics, including means, medians, ranges, and standard deviations (if numbers and distribution permit).

While the primary aim of this study is to evaluate the toxicity of palbociclib, patients will have disease evaluations performed as indicated in Section 8.1. Disease response will be assessed according to leukemia/lymphoma specific criteria (Section 12.0) and will be reported descriptively.

All these analyses will be descriptive and exploratory and hypotheses generating in nature.

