12.4.5 Response Criteria

12.4.5.1 Evaluation of Measurable Disease

- Complete Response (CR): Disappearance of all disease. CT or MRI should be free of residual mass or evidence of new disease. FDG-PET should be negative.
- CR unconfirmed (Cru): Residual mass is negative by FDG-PET; no new lesions by imaging examination; no new and/or progressive disease elsewhere
- Partial Response (PR): 50% decrease in SPD (the sum of the products of the largest diameter and the perpendicular diameter for a tumor mass) on CT or MRI; FDG-PET may be positive (Deauville score of 4 or 5 with reduced lesional uptake compared with baseline); no new and/or PD; morphologic evidence of disease may be present in BM if present at diagnosis; however, there should be 50% reduction in percentage of lymphoma cells
- Progressive Disease (PD): For those with > 25% increase in SPD on CT or MRI, Deauville score 4 or 5 on FDG-PET with increase in lesional uptake from baseline, or development of new morphologic evidence of disease in BM
- Stable Disease (SD): Neither sufficient shrinkage to qualify for PR nor sufficient increase to qualify for PD, taking as reference the smallest sum diameters while on study.

12.4.6 Evaluation of Non-measured Lesions (CT-based response, PET/CT based response not applicable)³⁶

- Complete Response (CR): Absent non-measured lesions.
- Partial response (PR): Absent/normal, regressed, lesions, but no increase.
- Stable Disease (SD): No increase consistent with progression
- Progressive Disease (PD): New or clear progression of preexisting non-measured lesions.

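### Read literally, Section 12.4.2 counts a lymphoma patient without measurable disease only if that patient progresses, so the LL response denominator depends on outcome

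*Combined protocol and SAP*

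**What the plan says.** Section 4.1.2 (Inclusion Criteria, Diagnosis) sets the entry condition: "Patients with LL must have either measurable or evaluable disease". Section 12.4.1 repeats it, so an LL patient whose disease is evaluable but not measurable can enrol.

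Section 12.4.2 defines who is evaluable for objective response. The main rule is "Only those patients who have measurable disease present at baseline and have received at least one dose of protocol therapy will be considered evaluable". A Note in parentheses follows: "Patients who exhibit objective disease progression prior to the end of Course 1 will also be considered evaluable". The Note does not mention measurable disease.

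Section 12.4.6 gives CR, PR, SD and PD definitions for disease that is not measured, under the title "Evaluation of Non-measured Lesions (CT-based response, PET/CT based response not applicable"). The first of them is "Complete Response (CR): Absent non-measured lesions".

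The Experimental Design Schema states "Each patient will receive a single cycle of therapy", so the end of Course 1 is the end of protocol therapy.

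Response serves secondary aim 1.2.1: "To preliminarily define the antitumor activity of palbociclib in combination with chemotherapy for children with relapsed ALL/LL". Section 11.5 sets the form of reporting: "Disease response will be assessed according to leukemia/lymphoma specific criteria (Section 12.0) and will be reported descriptively". No section gives another denominator for LL response.

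**The concern.** A dosed patient with measurable disease is evaluable under the main rule whatever happens next. Among dosed patients, the Note therefore enlarges the set only by those without measurable disease who progress. An evaluable-only patient who reaches CR, PR or SD has no route in, although Section 12.4.6 could classify that outcome and Section 8.1 already schedules LL imaging at baseline and, where baseline was positive, at Day 32.

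Membership of the denominator is then decided by the outcome, and only by failure. What is at stake is the LL response proportion reported for aim 1.2.1. Descriptive reporting does not cure this, because the proportion is what a reader will see, and with so few patients one outcome-dependent inclusion moves it visibly.

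**Working it through.** **No figure to reproduce.** The documents give no LL response rate, target or test, and no count of LL or evaluable-only patients. The check is algebra on the denominator, followed by an illustration with assumed inputs.

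**Notation (dosed LL patients).** m = patients with measurable disease, r = responders among them; e = evaluable-only patients, s = responders and p = progressors among those.

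- Literal Section 12.4.2 rate: r/(m+p)
- Measurable-only rate: r/m
- All-treated LL rate: (r+s)/(m+e)

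**Against the measurable-only rate.** Since p ≥ 0, r/(m+p) never exceeds r/m, and it is strictly lower whenever p ≥ 1 and r ≥ 1. Enumerating every configuration with m = 1 to 6 and e = 1 to 4 gave no exception.

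**Against all treated LL patients.** For e > p, the all-treated rate is a weighted average of r/(m+p), with weight m+p, and s/(e−p), with weight e−p. The literal rate is therefore lower exactly when s/(e−p) > r/(m+p), that is, when the excluded evaluable-only patients respond more often than the counted set.

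- If both groups share a response probability of 40% and 30% progress, the response probability among evaluable-only non-progressors is 0.40/(1 − 0.30) = 57%. The excluded group is enriched for responders, and downward is the expected direction.
- Example in that direction: m=4, r=2, e=2, s=1, p=1 gives 2/5 = 40% under the literal rule, against 2/4 = 50% measurable-only and 3/6 = 50% all treated.
- Reversal: m=4, r=2, e=2, s=0, p=1 gives 2/5 = 40% under the literal rule, against 2/6 = 33% all treated. This happens when evaluable-only patients rarely respond.

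**Expected size.** Assume response 40% and progression 30% in both groups, with patients independent. With e = 2, p is binomial (2, 0.30): P(0) = 0.49, P(1) = 0.42, P(2) = 0.09. The expected rate is the mean of 0.40m/(m+p).

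- m = 3: 0.49 × 1.2/3 + 0.42 × 1.2/4 + 0.09 × 1.2/5 = 0.196 + 0.126 + 0.0216 = 34.4%.
- m = 2: 0.49 × 0.8/2 + 0.42 × 0.8/3 + 0.09 × 0.8/4 = 0.196 + 0.112 + 0.018 = 32.6%.

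Both compare with an assumed true rate of 40%, a shortfall of about 6 to 7 percentage points. Dividing expected responders by the expected denominator gives 1.2/3.6 = 33% and 0.8/2.6 = 31%; those are ratios of expectations, not expected rates, and slightly overstate the effect.

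**The case against.** **The Note may be only a timing clarification.** It follows directly on a sentence about classifying patients with measurable disease, and can be read as saying that such a patient who progresses before the Day 32 evaluation still counts. On that reading the denominator does not depend on outcome. This stands as a possible intention, but the Note carries no such limit, and two analysts could build different denominators from the same data.

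**Eligibility may properly be wider than the response set.** The primary aims are MTD/RP2D, toxicity and pharmacokinetics, and Section 12.4.6 has a use for non-measured lesions in patients who also have measurable ones. This stands: excluding evaluable-only patients altogether would be a legitimate choice. Counting them only when they fail is not.

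**The effect is small.** Response is secondary, exploratory and descriptive, with no target or decision rule. An observed 1 of 3 has an exact 95% confidence interval of about 1% to 91%, far wider than a 6-point shift. This stands as to size. It does not justify leaving the rule as it is when the repair is nearly free.

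**A stronger reading is tempting.** A reader might infer that the plan certainly biases the LL response rate downward. The documents do not support that: the direction is certain only against a measurable-only denominator, under the literal reading, once an evaluable-only progressor is added and a measurable patient responds. Against all treated LL patients it can reverse, and the documents say nothing about whether the two groups respond alike.

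**Conclusion.** The point holds as a defect of wording with a real consequence. On its literal text, Section 12.4.2 makes the LL response denominator depend on outcome, because an evaluable-only patient is counted only on progression.

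The shortfall of roughly 6 to 7 points rests wholly on assumed counts, response and progression rates, and would differ with others; if no evaluable-only LL patient enrols, or none progresses, the rate equals the measurable-only rate. The issue is limited to LL, since ALL response is defined separately in Section 12.2, and to a descriptive secondary result. Nothing here touches the DLT assessment, the MTD or the RP2D.

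**What to change.** Replace the Section 12.4.2 rule and its Note with one rule that does not depend on outcome.

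- **Preferred:** every LL patient with measurable or evaluable disease at baseline who received at least one dose is response-evaluable. Early progression counts as PD, and evaluable-only disease is classified by Section 12.4.6. That section needs one clarification: its PR wording also covers absent lesions and so overlaps its CR, so state that complete absence is CR.
- **Equally acceptable:** restrict the rate to dosed patients with measurable disease, limit the Note to those patients, and list all evaluable-only outcomes, PD included, separately.

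The cost is a sentence or two of text and no added assessments. The first option makes the response criteria slightly more heterogeneous across LL patients; the second leaves evaluable-only patients out of the proportion but keeps their outcomes visible.

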12.4.3 Disease Parameters

12.4.3.1 Measurable disease:

A measurable node must have an LD_i (longest diameter) greater than 1.5 cm. A measurable extranodal lesion should have an LD_i greater than 1.0 cm. All tumor measurements must be recorded in millimeters (or decimal fractions of centimeters).

12.4.3.2 Non-measured disease:

All other lesions (including nodal, extranodal, and assessable disease) should be followed as nonmeasured disease (e.g., cutaneous, GI, bone, spleen, liver, kidneys, pleural or pericardial effusions, ascites).

12.4.3.3 Target lesions:

For patients staged with CT, up to six of the largest target nodes, nodal masses, or other lymphomatous lesions that are measurable in two diameters (longest diameter [LD_i] and shortest diameter) should be identified from different body regions representative of the patient's overall disease burden and include mediastinal and retroperitoneal disease, if involved.

12.4.4 Methods for Evaluation of Measurable Disease

All measurements should be taken and recorded in metric notation using a ruler or calipers. All baseline evaluations should be performed as closely as possible to the beginning of treatment and never more than 2 weeks prior to the beginning of the treatment.

The same method of assessment and the same technique should be used to characterize each identified and reported lesion at baseline and during follow-up. Imaging-based evaluation is preferred to evaluation by clinical examination unless the lesion(s) being followed cannot be imaged but are assessable by clinical exam.

12.4.4.1 Clinical lesions:

Clinical lesions will only be considered measurable when they are superficial (e.g., skin nodules and palpable lymph nodes) and ≥ 10 mm diameter as assessed using calipers (e.g., skin nodules). In the case of skin lesions, documentation by color photography, including a ruler to estimate the size of the lesion, is recommended.

12.4.4.2 Conventional CT and MRI:

The major response designations will be established by CT or MRI of involved sites in conjunction with morphologic evaluation of bone marrow (BM) if involved at diagnosis. With growing concerns about the risks of cumulative ionizing radiation exposure to children from CT, MRI could be considered as an alternative to CT for evaluating non-pulmonary disease sites. e.g., assessment of abdominal/pelvic disease. As with CT, if an MRI is performed, the technical specifications of the scanning sequences used should be optimized for the evaluation of the type and site of disease. Furthermore, as with CT, the modality used at follow-up should be the same as was used at baseline and the lesions should be measured/assessed on the same pulse sequence. It is beyond the scope of the response guidelines to prescribe specific MRI pulse sequence parameters for all scanners, body parts, and diseases. Ideally, the same type of scanner should be used and the image acquisition protocol should be followed as closely as possible to prior scans. Pulse sequences should include at a minimum, axial and coronal fat-saturated FRFSE-T2, coronal T1 and axial and coronal post-gadolinium fat-saturated T1 weighted imaging. Body scans should be performed with breath-hold scanning techniques, if possible.

12.4.4.3 PET-CT:

At present, the low dose or attenuation correction CT portion of a combined PET-CT is not always of optimal diagnostic CT quality. However, if the site can document that the CT performed as part of a PET-CT is of identical diagnostic quality to a diagnostic CT (with IV and oral contrast), then the CT portion of the PET-CT can be used for International Pediatric Non-Hodgkin Lymphoma Response Criteria measurements and can be used interchangeably with conventional CT in accurately measuring cancer lesions over time. Note, however, that the PET portion of the CT introduces additional data, which may bias an investigator if it is not routinely or serially performed.

12.4.4.4 Ultrasound:

Ultrasound is not useful in assessment of lesion size and should not be used as a method of measurement. Ultrasound examinations cannot be reproduced in their entirety for independent review at a later date and, because they are operator dependent, it cannot be guaranteed that the same technique and measurements will be taken from one assessment to the next. If new lesions are identified by ultrasound in the course of the study, confirmation by CT or MRI is advised. If there is concern about radiation exposure at CT, MRI may be used instead of CT in selected instances.

12.4.4.5 Endoscopy, Laparoscopy:

The utilization of these techniques for objective tumor evaluation is not advised. However, such techniques may be useful to confirm complete pathological response when biopsies are obtained or to determine relapse in trials where recurrence following complete response (CR) or surgical resection is an endpoint.

12.4.4.6 FDG-PET:

For patients with a positive PET scan at diagnosis, PET can be used to follow response in addition to a CT scan using the International Pediatric Non-Hodgkin Lymphoma Response Criteria.³⁴

12.4.5 Response Criteria

12.4.5.1 Evaluation of Measurable Disease

- Complete Response (CR): Disappearance of all disease. CT or MRI should be free of residual mass or evidence of new disease. FDG-PET should be negative.
- CR unconfirmed (Cru): Residual mass is negative by FDG-PET; no new lesions by imaging examination; no new and/or progressive disease elsewhere
- Partial Response (PR): 50% decrease in SPD (the sum of the products of the largest diameter and the perpendicular diameter for a tumor mass) on CT or MRI; FDG-PET may be positive (Deauville score of 4 or 5 with reduced lesional uptake compared with baseline); no new and/or PD; morphologic evidence of disease may be present in BM if present at diagnosis; however, there should be 50% reduction in percentage of lymphoma cells
- Progressive Disease (PD): For those with > 25% increase in SPD on CT or MRI, Deauville score 4 or 5 on FDG-PET with increase in lesional uptake from baseline, or development of new morphologic evidence of disease in BM
- Stable Disease (SD): Neither sufficient shrinkage to qualify for PR nor sufficient increase to qualify for PD, taking as reference the smallest sum diameters while on study.

12.4.6 Evaluation of Non-measured Lesions (CT-based response, PET/CT based response not applicable)³⁶

- Complete Response (CR): Absent non-measured lesions.
- Partial response (PR): Absent/normal, regressed, lesions, but no increase.
- Stable Disease (SD): No increase consistent with progression
- Progressive Disease (PD): New or clear progression of preexisting non-measured lesions.

12.4.7 Evaluation of organ enlargement³⁶

Complete Response (CR): Regress to normal

Partial response (PR): Spleen must have regressed by > 50% in length beyond normal

Stable Disease (SD): No increase consistent with progression

Progressive Disease (PD): In the setting of splenomegaly, the splenic length must increase by 50% of the extent of its prior increase beyond baseline. If no prior splenomegaly, must increase by at least 2 cm from baseline.

New or recurrent splenomegaly

12.4.8 Duration of Response

12.4.8.1 Duration of overall response:

The duration of overall response is measured from the time measurement criteria are met for CR or PR (whichever is first recorded) until the first date that recurrent or progressive disease is objectively documented (taking as reference for progressive disease the smallest measurements recorded since the treatment started).

The duration of overall CR is measured from the time measurement criteria are first met for CR until the first date that progressive disease is objectively documented.

12.4.8.2 Duration of stable disease:

Stable disease is measured from the start of the treatment until the criteria for progression are met.

12.4.8.3 Progression-Free Survival

PFS is defined as the duration of time from start of treatment to time of progression or death, whichever occurs first.

12.4.8.4 Response Review

Response will be as per institutional evaluations.

13.0 **ADVERSE EVENT REPORTING REQUIREMENTS**

Adverse event data collection and reporting which are required as part of every clinical trial, are done to ensure the safety of patients enrolled in the studies as well as those who will enroll in future studies using similar agents. Adverse events are reported in a routine manner at scheduled times during a trial. (Please follow directions for routine reporting provided in the Case Report Forms for this protocol). Additionally, certain adverse events must be reported in an expedited manner to allow for optimal monitoring of patient safety and care. The following sections provide information about expedited reporting.

Reporting requirements may include the following considerations: 1) whether the patient has received an investigational or commercial agent; 2) whether the adverse event is considered serious; 3) the grade (severity); and 4) whether or not hospitalization or prolongation of hospitalization was associated with the event.

An investigational agent is a protocol drug administered under an Investigational New Drug Application (IND). In some instances, the investigational agent may be available commercially, but is actually being tested for indications not included in the approved package label.

Commercial agents are those agents not provided under an IND but obtained instead from a commercial source. The NCI, rather than a commercial distributor, may on some occasions distribute commercial agents for a trial.

13.1 Steps to Determine If an Adverse Event Is To Be Reported In an Expedited Manner

Step 1: Identify the type of adverse event using the NCI CTCAE version 5.0. The descriptions and grading scales found in the revised CTCAE version 5.0 will be used for AE reporting. All appropriate treatment areas should have access to a copy of the CTCAE version 5.0. A copy of the CTCAE version 5.0 can be downloaded from the CTEP website (<http://ctep.cancer.gov>).

Step 2: Grade the adverse event using the NCI CTCAE.

Step 3: Review Table A in this section to determine if:

- the adverse event is considered serious;
- there are any protocol-specific requirements for expedited reporting of specific adverse events that require special monitoring; and/or
- there are any protocol-specific exceptions to the reporting requirements.

NOTE: This includes all events that occur within 30 days of the last dose of protocol treatment. Any event that occurs more than 30 days after the last dose of treatment and is attributed (possibly, probably, or definitely) to the agent(s) must also be reported according to the instructions in the table below. Attribution categories are as follows: Unrelated, Unlikely, Possible, Probable, and Definite.

Step 4: Complete the MedWatch Form FDA 3500A SAE Report found on the protocol homepage and load into RAVE per the CRF guidelines. **CTEP AERS will NOT be used for reporting of Serious Adverse Events**

Table A: Phase 1 and Early Phase 2 Studies: Expedited Reporting Requirements for Adverse Events that Occur on Studies under an IND/IDE within 30 Days of the Last Administration of the Investigational Agent/Intervention^{1,2}

FDA REPORTING REQUIREMENTS FOR SERIOUS ADVERSE EVENTS (21 CFR Part 312) NOTE: Investigators MUST immediately report to the sponsor ANY Serious Adverse Events, whether or not they are considered related to the investigational agent(s)/intervention (21 CFR 312.64) An adverse event is considered serious if it results in ANY of the following outcomes:
 
 1) Death 2) A life-threatening adverse event 3) An adverse event that results in inpatient hospitalization or prolongation of existing hospitalization for ≥ 24 hours 4) A persistent or significant incapacity or substantial disruption of the ability to conduct normal life functions 5) A congenital anomaly/birth defect.

6) Important Medical Events (IME) that may not result in death, be life threatening, or require hospitalization may be considered serious when, based upon medical judgment, they may jeopardize the patient or subject and may require medical or surgical intervention to prevent one of the outcomes listed in this definition. (FDA, 21 CFR 312.32; ICH E2A and ICH E6).		
ALL SERIOUS adverse events that meet the above criteria MUST be immediately reported via MedWatch Form FDA 3500A within the timeframes detailed in the table below.		
Hospitalization	Grade 1 and Grade 2 Timeframes	Grade 3-5 Timeframes
Resulting in Hospitalization ≥ 24 hrs	7 Calendar Days	24-Hour 5 Calendar Days
Not resulting in Hospitalization ≥ 24 hrs	Not required	
Expedited AE reporting timelines are defined as: 
 ○ “24-Hour; 5 Calendar Days” - The AE must initially be reported via MedWatch within 24 hours of learning of the AE, followed by a complete expedited report within 5 calendar days of the initial 24-hour report. ○ “7 Calendar Days” - A complete expedited report on the AE must be submitted within 7 calendar days of learning of the AE. 		

¹Serious adverse events that occur more than 30 days after the last administration of investigational agent/intervention and have an attribution of possible, probable, or definite require reporting as follows: Expedited 24-hour notification followed by complete report within 5 calendar days for:
 
 • All Grade 3, 4, and Grade 5 AEs 
Expedited 7 calendar day reports for:
 
 • Grade 2 AEs resulting in hospitalization or prolongation of hospitalization 
² For studies using PET or SPECT IND agents, the AE reporting period is limited to 10 radioactive half-lives, rounded UP to the nearest whole day, after the agent/intervention was last administered. Footnote “1” above applies after this reporting period.
 
Effective Date: May 5, 2011
		

- Any medical event equivalent to CTCAE grade 3, 4, or 5 that precipitates hospitalization (or prolongation of existing hospitalization) must be reported regardless of attribution and designation as expected or unexpected with the exception of any events identified as protocol-specific expedited adverse event reporting exclusions.
- Any event that results in persistent or significant disabilities/incapacities, congenital anomalies, or birth defects must be reported via MedWatch Form FDA 3500A in RAVE if the event occurs following treatment with an agent under a COG IND.

